5.4.1.1 Mean Amblyopic Eye VA at 4 Weeks

For both age cohorts, the primary objective is to compare the efficacy of 4 weeks of treatment with
1 hour/day of binocular game play 5 days per week plus spectacle correction to treatment with
spectacle correction alone (subsequently referred to as "control" treatment).

978

An analysis of covariance (ANCOVA) will be performed to compute the 4-week mean change in
amblyopic-eye VA for the binocular and control treatments, adjusted for baseline acuity, and a 95%
confidence interval will be constructed on the treatment group difference.

982

The primary analysis will follow a modified intent-to-treat principle. Data will be included only from subjects who complete the 4-week exam within the pre-defined analysis window. There will be no imputation of data for subjects who are lost to follow-up or withdraw from the study prior to the 4-week exam. Multiple imputation for missing data will be performed as a secondary approach, and results of the analysis with imputation of missing data assessed for consistency with the primary analysis.

988 989

993

994

996

990 Additional approaches to the primary analysis include the following:

- Limit the analysis to subjects whose 4-week outcome exams were performed within the protocol window (3 to 5 weeks post-randomization)
 - Include subjects who completed the 4-week exam outside of the pre-defined analysis window
- 995 5.4.2 Secondary Analyses

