- 87 If these cases account for $\ge 10\%$ of the data, a sensitivity analysis will be performed in which analyses are
- 88 repeated after substituting missing values for these cases.
- 89
- A logarithm (base 10) transformation will be applied to stereoacuity scores for analyses. Participants
- 91 classified as having nil stereoacuity (worse than 2000 seconds of arc) will be assigned a log score of 3.6
- 92 (the next largest disparity level) to calculate the difference between log converted scores (baseline –
- 93 follow-up).
- 94

98

95 **3.3 Analysis Window**

- 96 The analysis window for visits will be as follows:
- 4-week: 3 to <7 weeks (21 to <49 days) after randomization
 - 8-week: 7 to <15 weeks (49 to <105 days) after randomization
- 99 16-week (visit occurring 8 weeks after initiating binocular treatment for participants initially assigned to spectacles only group): 15 to <23 weeks (105 to <161 days) after randomization
 101

- 102 A visit will be considered missed if it is completed outside of the analysis window or not completed at all.
- 103 Analyses of the amblyopic-eye VA and stereoacuity outcomes will be limited to visits completed within
- 104 the analysis windows.
- 105 106

107 4.0 Analysis Plan for 8-week Randomized Trial Phase

- Analyses outlined in this chapter are limited to data collected at the time of randomization (subsequently 108 referred to as 'baseline') through the 8-week post-randomization follow-up visit. 109
- 110

113

114

111 **4.1 Primary Analysis**

- 112 Two treatment approaches will be evaluated within each of the sub-studies:
 - Binocular treatment: Binocular 'Dig Rush' game played on an iPad device 1 hour per day 5 days per week and spectacle wear (if required)
 - Continued spectacle wear (if required) only •
- 115 116

117 The primary analysis will follow a modified intent-to-treat principle, limited to data from participants who complete the 4-week exam within the pre-specified analysis windows as defined in section 3.3. Data 118 119 from participants with treatment crossover, those who received alternative treatment for ≥ 1 week and participants found to be ineligible after subsequent review of enrollment data will also be included in the 120 primary analysis. There will be no imputation of data for participants who are lost to follow-up or 121 122 withdraw from the study prior to the 4-week exam.

123

124 An analysis of covariance (ANCOVA) adjusting for baseline VA will be performed to compute the 4-

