- 155 1. Perform multiple imputation using the Monte Carlo Markov Chain (MCMC) method that
- includes data from baseline and follow-up visits to impute 4-week VA data for participants whomissed the exam
- Exclude 4-week VA data from participants who completed the 4-week exam outside of the
 protocol window (4 ± 1 week after randomization)
- 160 3. Exclude 4-week VA data from participants found to be ineligible upon subsequent review of
 161 enrollment data, those with treatment crossover, or those who received alternative treatment for ≥
 162 1 week
- 163 4. Include cause of amblyopia as an adjustment covariate in the ANCOVA model
- 164 5. Winsorize baseline and 4-week VA data at the 10th and 90th percentiles by treatment group
 165 (younger cohort only)
- 166
- 167 If the primary analysis and sensitivity analyses produce similar results, the primary analysis will be168 considered the definitive analysis and the sensitivity analyses will be used to provide supportive evidence
- 169 of the magnitude of treatment effect. However, if the results differ, exploratory analyses will be
- 170 performed to evaluate the factors that have contributed to the differences.
- 171

172 4.2 Secondary Analyses

- Secondary analyses will be conducted separately for each sub-study and all treatment group comparisons
 will consist of a 2-sided test of the null hypothesis of no difference between groups. Unless otherwise
 specified, analyses will only include participants with visits completed within the pre-specified analysis
- 176 windows (section 3.3) and will follow the principles outlined in the primary analysis.
- 177

178 Due to the number of secondary outcomes, the 2-sided type I error rate for each secondary analysis

- (including confidence intervals calculated on the estimate) will be adjusted to account for multiple testingas follows:
- The Bonferroni method will be used to preserve the overall type 1 error rate at 5% (4.9% for the younger cohort; see section 4.1) for all secondary analyses of visual acuity (n=3 tests, sections 4.2.1 4.2.2) and at 5% across all stereoacuity analyses (n=4 tests, section 4.2.4)
- For each subgroup analysis (section 4.2.3), statistical significance of the interaction term will be tested using a type I error rate of 1%.
- 186

187 4.2.1 Visual Acuity Improvement at 8 Weeks

- A treatment group comparison of mean VA change from baseline to 8 weeks will parallel the 4-week

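### The SAP drops the protocol's pre-specified analysis that includes 4-week exams done outside the analysis window, so no planned amblyopic-eye acuity analysis uses every 4-week acuity measured

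*SAP*

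**What the plan says.** **Protocol 5.4.1.1** confines the primary analysis to "subjects who complete the 4-week exam within the pre-defined analysis window", without imputation. It adds multiple imputation as a secondary approach, then lists two further approaches. One limits the analysis to exams 3 to 5 weeks after randomization. The other reads "Include subjects who completed the 4-week exam outside of the pre-defined analysis window".

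**SAP 3.3** sets the windows as "4-week: 3 to <7 weeks (21 to <49 days) after randomization" and "8-week: 7 to <15 weeks (49 to <105 days) after randomization". It then states: "A visit will be considered missed if it is completed outside of the analysis window or not completed at all". Its last sentence begins "Analyses of the amblyopic-eye VA and stereoacuity outcomes will be limited to visits completed within" and ends with the analysis windows.

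**SAP 4.1** takes for the primary analysis those "who complete the 4-week exam within the pre-specified analysis windows as defined in section 3.3", again without imputation. Of its five sensitivity analyses, item 1 uses multiple imputation "to impute 4-week VA data for participants" who missed the exam, and item 2 narrows the set to 4 ± 1 week. Items 3 to 5 exclude ineligible, crossover or alternatively treated participants, adjust for cause of amblyopia, and winsorize (younger cohort only).

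**The concern.** The primary set is selected on something that happens after randomization: whether the child attended inside the window. The protocol planned to check that selection in both directions, once by tightening the window and once by ignoring it. The SAP keeps only the tightening. The check that uses measured data from the children left out of the primary analysis has gone, and the SAP's revision history does not mention the omission.

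This matters because SAP 4.1 treats the primary result as definitive when the sensitivity analyses agree with it. Every amblyopic-eye analysis in that list either leaves out the children with out-of-window exams or, on the reading set out below, replaces their acuity with a modelled value. Agreement among these analyses therefore cannot show whether the window rule affects the result. If early or late attendance is related to engagement with the game, the children left out could differ between arms.

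**Working it through.** **Text comparison.** The SAP names Protocol Version 4.0 as its basis, so the two lists should correspond.

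- Primary analysis, in-window exams only: in both documents.
- Multiple imputation: in both.
- Narrow to 4 ± 1 week: in both (SAP item 2).
- Add out-of-window exams: protocol only. No SAP item does this, and the last sentence of SAP 3.3 forbids it.

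**Which exams are affected.** Those before day 21 or from day 49 on.

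- An exam on day 20 lies in no analysis window, so its amblyopic-eye acuity enters no planned outcome comparison.
- An exam on day 49 that was done as the 4-week visit lies in the adjoining 8-week window. The SAP does not say how it is then classified.

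**Imputation.** Item 1 imputes for participants who missed the exam. SAP 3.3 defines a missed visit to include one completed outside the window. Read together, a child tested on day 20 receives an imputed 4-week value although one was measured. This is an inference from two sections; item 1 does not say it outright.

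**Size.** No figure in the plan is in dispute. As background, a two-sample t-test with 90% power, two-sided 5%, difference 0.75 line and SD 1.5 needs 172 (noncentral t), as in Protocol Table 2. Per arm 86/0.95 = 90.5, rounded up to 91, gives the stated 182.

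Let f be the share of examined children who are out of window, taken as equal in the two arms, and let gap be the in-window treatment effect minus the out-of-window effect. Ignoring covariate adjustment:

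- all-observed effect = (1 − f) × in-window effect + f × out-of-window effect
- in-window estimate − all-observed estimate = f × gap

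Neither f nor gap is in the documents. Assumed ranges:

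- f = 0.01, gap = 0.5 line: 0.01 × 0.5 = 0.005 line
- f = 0.05, gap = 1.5 lines: 0.05 × 1.5 = 0.075 line
- no effect at all in the out-of-window children (gap = 0.75), f = 0.03 to 0.10: 0.0225 to 0.075 line

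Against the planned 0.75 line, 0.005 to 0.075 is 0.7% to 10%.

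For scale, the standard error of the difference is about:

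- younger cohort, N = 182, observed SD 1.6 lines: 1.6 × √(4/182) = 0.24 line
- older cohort, N = 116, SD 6 letters: 6 × √(4/116) = 1.11 letters

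At 5 letters per line, 0.075 line is 0.375 letter. The largest shift is therefore about a third of a standard error in either cohort (0.075/0.24 = 0.31; 0.375/1.11 = 0.34).

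**The case against.** The strongest reply is that the protocol's own primary analysis also excludes out-of-window exams, so the SAP's primary analysis agrees with it and only a supplementary check is missing. The 4-week analysis window already runs two weeks beyond the protocol's 3 to 5 weeks, so few exams should fall outside it. Item 2 also tests sensitivity to timing. All of this is correct and limits the severity. It does not explain why a pre-specified analysis was left out, and item 2 removes children, so it says nothing about those already removed.

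A reader might infer more than the documents support:

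- *That no analysis of any kind uses out-of-window exams.* SAP 4.4 includes all completed visits in the safety analyses regardless of window. The acuity outcome there is the fellow eye, so the point is confined to amblyopic-eye acuity.
- *That the primary result rests on imputed values.* It does not. Only item 1 imputes, and its model uses baseline and follow-up data.
- *That nothing planned would reveal unequal attendance.* SAP 4.5 plans a participant flow chart, completion rates and protocol deviations by arm. These would show unequal completion, but not its effect on acuity.
- *That every late exam is thrown away.* An exam from day 49 lies in the 8-week window, and its classification is unstated.

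**Conclusion.** The point holds for amblyopic-eye acuity. The SAP omits, without a stated reason, an analysis that the protocol pre-specifies, and SAP 3.3 as written bars it. That finding rests on the text alone and is firm. That item 1 imputes over measured acuities follows from applying the SAP 3.3 definition to item 1. It is the natural reading, but the SAP should confirm or correct it.

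The likely effect on the estimate is small: 0.005 to 0.075 line against 0.75 under the assumed 1% to 5% out of window, equal shares by arm, and a gap of 0.5 to 1.5 lines. A reader might infer that the trial's treatment effect is materially biased. The documents give neither the number of affected exams nor their outcomes, so they do not support that. The omitted analysis would measure the effect of the window rule directly. This should be corrected because the correction is cheap and the check was promised; it does not put the primary analysis in doubt.

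**What to change.** 1. In SAP 4.1, add a sensitivity analysis that repeats the primary ANCOVA with all completed 4-week exams, whatever the day, and exempt it from the last sentence of SAP 3.3.
2. In item 1, impute only when no 4-week exam was done; otherwise use the observed acuity.
3. State that an exam from day 49 on that was done as the 4-week visit counts as the 4-week exam in this sensitivity analysis, and that the same exam is not also used as the 8-week outcome.
4. Report the number of out-of-window 4-week exams by arm.

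The cost is a few sentences, one more model run and one more row in a table. The data are already collected, and the primary analysis is unchanged.

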- 317 Only 22% of subjects randomized to the binocular game performed >75% of the prescribed
- 318 treatment (median 46%, interquartile range 20% to 72%). In younger subjects 5 to <7 years of
- 319 age, without prior amblyopia treatment, amblyopic-eye VA improved 2.5 ± 1.5 lines in the
- 320 binocular group and 2.8 ± 0.8 in the patching group. Adverse effects (diplopia, reduction of
- 321 fellow-eye VA, new tropia) were uncommon and of similar frequency between groups.
- 322
- 323 We therefore concluded that in children 5 to <13 years of age, amblyopic-eye VA improved
- 324 with both binocular game play and patching, particularly in younger children age 5 to <7 years
- 325 without prior amblyopia treatment. However, based on a post hoc analysis, VA improvement
- 326 with this particular binocular iPad treatment was not as good as with 2 hours of prescribed daily
- 327 patching.

328 1.3 **Rationale for Proposed Study Design**

329 It is entirely possible that our failure to find non-inferiority of binocular treatment to part-time

- 330 patching in our recent RCT was due to poor compliance with the binocular treatment. Only 22%
- 331 of subjects randomized to the binocular game performed >75% of the prescribed treatment
- 332 (median 46%, interquartile range 20% to 72%).
- 333

- 334 Recently, a new binocular game has been developed for children, called "Dig Rush," which is
- much more interesting than the falling blocks game because it involves more interesting tasks
- such as digging for gold and earning rewards. It has 42 levels, and therefore the child remains
- and engaged for a much longer period of time than the falling blocks game.
- 338
- 339 The Birch group has studied the binocular Dig Rush game in children age 4 to <10 years and
- found that compliance with the game is excellent, with a mean amblyopic eye VA improvement of 1.5 lines at 2 weeks and 1.7 lines at 4 weeks.²⁶
- 342

355

362

363

364

365

367

381

- 343 Based on several promising pilot studies of binocular treatment in children and in adults, a full
- RCT is warranted, to investigate whether binocular treatment is an effective treatment for
- amblyopia, and, analogous to the PEDIG RCT which investigated the effectiveness of
- 346 patching,²⁷ the appropriate control group is continued spectacle treatment alone.

347 **1.4 Study Objective**

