- 847 (95% confidence interval (CI): 1.07 to 1.58 logMAR lines).
- 848

849 Given the more stringent criteria for assessing VA stability with spectacles and shorter outcome

850 time in the current study as compared to the previous study, we anticipate that the magnitude and

851 standard deviation of VA improvement after 4 weeks in the current study will be smaller than those

- 852 in Table 1.
- 853
- 854 Binocular Treatment Group (Dig Rush Game):
- 855 Data from 2 studies were reviewed: (1) preliminary pilot data for subjects randomly assigned to 4
- 856 weeks of binocular treatment with the Dig Rush game on an iPad device (E. Birch Study) and (2)

857 data from a previous PEDIG trial (ATS18) for subjects randomly assigned to binocular treatment

858 with the Hess falling blocks game on an iPad device (Table 1). Based on the more conservative

- 859 estimates from ATS18, a mean VA change at 4 weeks of 1.09 lines (95% CI: 0.63 to 1.55 lines),
- with standard deviation 1.32 logMAR lines (95% CI: 1.06 to 1.74 logMAR lines) after adjusting for 860
- 861 baseline VA might be expected. However, we anticipate that the magnitude of VA improvement
- 862 after 4 weeks in the current study will be somewhat larger than that in ATS18, due to better
- 863 compliance.
- 864 865

	J	Change in Amblyopic Eye VA			
		at the 4 or 5 Week Visit			
		(logMAR Lines) [‡]			
Cohort	Ν	Mean Change (95% CI)	SD Change (95% CI)		
Spectacle Correction Alone:					
ATS5: Age 3 to <7 years [†]	53	0.55 (0.19 to 0.90)	1.28 (1.07 to 1.58)		
No prior amblyopia treatment	50	0.54 (0.17 to 0.91)	1.32 (1.10 to 1.64)		
Prior amblyopia treatment	3	0.67 (-2.21 to 3.54)	0.39 (0.20 to 2.45)		
Binocular Treatment:					
E. Birch Study (Age 4 to <7 years) ^	9	1.67 (0.73 to 2.61)	1.19 (0.80 to 2.28)		
ATS18 (Age 5 to <7 years) §	34	1.09 (0.63 to 1.55)	1.32 (1.06 to 1.74)		
No prior amblyopia treatment	19	1.47 (0.73 to 2.22)	1.54 (1.16 to 2.28)		
Prior amblyopia treatment	15	0.60 (0.15 to 1.05)	0.81 (0.59 to 1.28)		

866 Table 1: Previous Study Data from Subjects Aged 3 to <7 Years of Age

[‡] Positive values indicate improvement. Mean and SD adjusted for baseline visual acuity.

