27 the primary objective is to compare mean change in amblyopic-eye visual acuity (VA) between

28 prescribed binocular game play with spectacle wear (if needed) and continued spectacle wear (if needed)

alone (subsequently referred to as the "binocular group" and "control group") after 4 weeks of treatment.

30 A secondary analysis will compare mean change in amblyopic-eye VA after 8 weeks of treatment.

31 32

33 2.0 Sample Size / Re-estimation

A minimum sample size was calculated to be 116 participants in the younger cohort and 84 participants in

- the older cohort based on the primary treatment group comparison of mean VA change from baseline to 4
- 36 weeks. The sample size was estimated to provide 90% power to detect a treatment group difference in
- mean VA for each sub-study assuming a 2-sided type I error rate of 5%, a group difference of 0.75
- 38 logMAR lines (pooled standard deviation (SD) = 1.2 logMAR lines) in the younger age cohort, a group
- difference of 3.75 letters (pooled SD = 5 letters) for the older age cohort, including a 5% adjustment for
- 40 loss to follow-up. Details of the sample size estimation are described in a separate document
- 41 (F:\user\PEDIG\Studies\ATS\Protocols\Current Protocols\Binocular Game Play ATS20\Sample
- 42 Size\Verification\Binocular Games Sample Size 10-05-16.docx).
- 43 Although we believe our estimates of variance are reasonable, a sample size re-estimation will be
- 44 performed for each sub-study once approximately 50% of the pre-planned sample has completed the 4-
- 45 week outcome visit. A pooled estimate of variance without respect to treatment group will be calculated
- 46 and used to re-estimate sample size using a procedure that maintains masking and has a negligible effect
- 47 on the Type I error rate.¹ Within each sub-study, if the observed standard deviation of change is larger
- 48 than the anticipated estimate, the sample size will be increased up to a maximum limit of 182 participants
- 49 (SD of change = 1.5 logMAR lines) and 206 participants (SD of change = 8 letters) for the younger and
- 50 older cohorts, respectively, which includes a 5% loss to follow-up. Due to the short duration of the
- 51 primary outcome (4 weeks) and expected rapid recruitment, no interim monitoring will be conducted for
- either sub-study. This decision will be re-evaluated if the sample size is increased or the recruitment ratesare slower.
- 55

55 **2.1 Interim Monitoring (Younger Cohort)**

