- 125 week mean change in amblyopic-eye VA for each treatment group and the 95% confidence intervals
- 126 (CIs), as well as the difference in mean VA change between the treatment groups and the 95% CI.
- 127

128 For the younger cohort, the type I error rate for the primary analysis is pre-specified as 4.9% in the

Interim Monitoring Plan (section 2.1) because 0.1% was allocated for the review of VA outcomes by the 129 130 Data and Safety Monitoring Committee. Therefore, the significance level of the confidence intervals will

- 131 be adjusted to 95.1%.
- 132

Model Assumptions: Model assumptions for the ANCOVA will be assessed, including linearity of 133

- adjustment covariates, normality and equal variance of the outcome across the treatment groups. The 134
- linearity assumption of covariates will be evaluated using descriptive scatterplots and by categorizing 135
- each of the baseline factors in the model to check for approximate linearity of the coefficients across 136
- ordered categories. A covariate will be included as a continuous variable in the model if assumptions for 137
- 138 linearity are met for that covariate; otherwise, it will be categorized.
- 139
- 140 Although the ANCOVA is relatively robust to departures from normality, potential outliers will be
- identified and a sensitivity analysis will be performed to evaluate the effect of these outliers on the 141 142
- primary outcome results. Residual values will be examined for an approximate normal distribution. If
- values are highly skewed, then either a transformation will be applied or alternative analysis strategies 143 (robust regression, non-parametric methods) will be considered instead.
- 144 145
- Confounding: Imbalances between groups in important baseline covariates are not expected to be of 146
- sufficient magnitude to produce confounding. However, as a complement to the primary analysis, the 147
- 148 presence of confounding will be evaluated. If there is evidence of confounding based on one or more

- 149 factors, the primary analysis will be repeated with the factors included in the ANCOVA model as
- adjustment covariates. Results of the model will be compared with that of the primary analysis results to
- evaluate the effect of confounding on the treatment group comparison.
- 152
- 153 Sensitivity Analyses:
- 154 The primary analysis will be repeated in the following ways:

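### The primary ANCOVA adjusts only for baseline acuity and omits prior amblyopia treatment, giving up a small, nearly free gain in precision

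*SAP*

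**What the plan says.** The primary model has a single covariate. SAP 4.1 states: "An analysis of covariance (ANCOVA) adjusting for baseline VA will be performed to compute the 4"-week mean change in each group. Protocol 5.4.1.1 describes the same model, and SAP 4.2.1 has the 8-week comparison of means parallel it.

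Other covariates appear in four places, none of them the primary model:

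- SAP 4.1, sensitivity item 4: "Include cause of amblyopia as an adjustment covariate in the ANCOVA model".
- SAP 4.1, Confounding: the primary ANCOVA is repeated with further factors if confounding is found. No factor and no criterion is named.
- SAP 4.2.3: subgroup models with a main effect and an interaction, including prior treatment and age. A formal analysis needs at least 20 participants per category in each arm.
- SAP 4.2.3, younger cohort only: an exploratory comparison of game algorithms adjusted for baseline VA and age.

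History of prior treatment is collected at enrolment (Protocol 2.3). Randomisation is stratified by amblyopic-eye VA alone within each age cohort (Protocol 2.5).

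On size, SAP 2.0 says: "The sample size was estimated to provide 90% power to detect a treatment group difference in" mean VA, with 0.75 "logMAR lines (pooled standard deviation (SD) = 1.2 logMAR lines) in the younger age cohort, a group" difference of 3.75 letters (SD 5) in the older cohort. On the significance level, SAP 4.1 says: "For the younger cohort, the type I error rate for the primary analysis is pre-specified as 4.9% in the" interim monitoring plan.

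**The concern.** The protocol itself treats prior treatment as prognostic. Section 1.2 reports improvement "with both binocular game play and patching, particularly in younger children age 5 to <7 years" without prior treatment. Tables 1 and 3 split earlier trial data by prior treatment, and section 5.2.2 reweights the ATS3 control data by it to set the older-cohort assumption.

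A baseline factor that predicts change beyond baseline VA, if left out, stays in the error term and widens the confidence interval. A chance imbalance in it also stays in the primary estimate. This matters most in the younger cohort. The pooled SD at re-estimation was 1.6 lines, the sample is capped at the 182 that corresponds to 1.5, and more children are not an available remedy.

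The existing provisions do not supply the gain. The confounding clause acts only after an imbalance is seen. In the older cohort the subgroup model would probably not run: at the 17% without prior treatment expected in Table 3, 58 per arm gives 0.17 × 58 ≈ 10 per arm, below the 20 required.

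**Working it through.** **1. Reproduce the plan's figures.** Two-sample t-test, two-sided 5%, 90% power:

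- 0.75 lines, SD 1.2: 110 completers; 110/0.95 = 115.8, so 116.
- 0.75 lines, SD 1.5: 172 (86 per arm); the plan gives 182 with loss to follow-up.
- 3.75 letters, SD 5: 78. SD 6: 110 (55 per arm), so 116.

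All match Tables 2 and 4 and the re-estimated totals. The earlier-trial SDs behind them are described in the table footnotes as adjusted for baseline VA, so the design power already matches a model with that covariate alone.

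**2. Variance explained by prior treatment.** With *p* the share without prior treatment, *d* the difference in mean change (no prior minus prior) and SD the printed total SD:

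R² = p(1 − p)d² / SD²

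Because the means and SDs are acuity-adjusted, this is variance explained beyond baseline VA. The documents state no R²; these values are derived.

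| Source | n without / with | Means | p(1 − p)d² | SD² | R² | Welch p |
|---|---|---|---|---|---|---|
| ATS18 younger, binocular (lines) | 19 / 15 | 1.47 v 0.60 | 0.2465 × 0.87² = 0.187 | 1.32² = 1.742 | 10.7% | 0.04 |
| ATS5 younger, spectacles (lines) | 50 / 3 | 0.54 v 0.67 | 0.0534 × 0.13² = 0.0009 | 1.28² = 1.638 | 0.06% | 0.67 |
| ATS3 older, spectacles (letters) | 27 / 40 | 3.4 v 0.9 | 0.2406 × 2.5² = 1.504 | 5.3² = 28.09 | 5.4% | 0.06 |
| ATS18 older, binocular (letters) | 22 / 96 | 2.3 v 1.7 | 0.1517 × 0.6² = 0.055 | 5.1² = 26.01 | 0.2% | 0.67 |

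At the 17/83 mix expected for this trial, ATS3 gives 0.1411 × 2.5² = 0.882, and 0.882/28.09 = 3.1%. With the total variance built from the subgroup SDs instead (0.17 × 5.7² + 0.83 × 4.6² + 0.882 = 23.97), it is 3.7%.

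**3. Average over the arms.** A single main effect recovers roughly the average of the two arms' differences: (0.87 − 0.13)/2 = 0.37 lines in the younger cohort and (2.5 + 0.6)/2 = 1.55 letters in the older. For an assumed share without prior treatment of 17% to 56%, R² is about 1.3% to 2.4% at the design SDs (1.2 lines, 5 letters) and about 0.8% to 1.7% at the re-estimated SDs (1.6 lines, 6 letters). A plausible range is therefore 1% to 5%, with 0% and about 10% as the extremes.

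**4. Power.** Residual SD = SD × √(1 − R²), noncentral t.

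| R² | Younger: 86 per arm, SD 1.6, 0.75 lines, alpha 4.9% | Older: 55 per arm, SD 6, 3.75 letters, alpha 5% | Confidence interval narrower by |
|---|---|---|---|
| 0 | 86.2% | 90.1% | – |
| 1% | 86.5% | 90.4% | 0.5% |
| 3.1% | 87.2% | 91.0% | 1.6% |
| 5.4% | 88.0% | 91.6% | 2.7% |
| 10.7% | 89.7% | not supported by older-cohort data | 5.5% |

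In the younger cohort, R² of 1% to 5% is worth 172 × R²/(1 − R²), or about 2 to 9 completers.

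**5. Chance imbalance.** If the larger table difference held in both arms, the 95% range of the shift in the unadjusted estimate is ±1.96 × d × √(2p(1 − p)/n). Younger: 1.96 × 0.87 × √(2 × 0.559 × 0.441/86) = ±0.13 lines. Older: 1.96 × 2.5 × √(2 × 0.17 × 0.83/55) = ±0.35 letters. These are upper-end figures, about 17% and 9% of the target differences. They are part of the ordinary sampling error in step 4, not an addition to it.

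**The case against.** The strongest reply is that the model is valid and matches its design. Omitting a prognostic covariate does not bias a randomised comparison, and the sample sizes reproduce from planning data adjusted for baseline VA alone. A reader might infer a biased estimate or a failed power claim; the documents support neither. This reply stands, and it limits the point to efficiency.

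The evidence is also uneven: clear in one comparison of 19 v 15 children, borderline in one, and negligible or absent in two. Applying the most favourable arm's R² to a whole cohort would overstate the gain. This stands too, and it is why the plausible range is 1% to 5%.

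Three further inferences are tempting:

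- *Age should be a required covariate as well.* The documents give no within-cohort age effect, and the contrast between younger and older children is already removed by analysing the cohorts separately.
- *Cause of amblyopia is the only added covariate in the plan.* The confounding clause and the models in SAP 4.2.3 show otherwise.
- *The younger cohort is definitely underpowered, and this would repair it.* The SD of 1.6 comes from 51 children with a confidence interval of 1.2 to 2.0, and the documents do not say whether it is adjusted for baseline VA. If it is a raw SD, the planned ANCOVA already recovers part of it.

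Finally, timing. According to its revision history, SAP 2.0 was revised during manuscript review and SAP 4.0 while the younger-cohort manuscript was being drafted. Changing the primary covariates after outcomes are known would be worse than leaving them alone. This stands and shapes the fix.

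**Conclusion.** The point holds as a modest efficiency gain, not as an error. The plan leaves out of its primary model a recorded, unstratified baseline factor that the sponsor itself treated as prognostic, and no other provision reliably brings that factor in. The plausible gain is about 0.3 to 1.8 power points in the younger cohort and 0.3 to 1.5 in the older, with an upper limit of about 3.5 points in the younger cohort if the ATS18 younger figure held in both arms.

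This assumes a prior-treatment mix between the 17% and 56% without prior treatment seen in the tables, differences similar to those in the earlier trials, 5% loss to follow-up, and the re-estimated SDs of 1.6 lines and 6 letters taken as residual SDs.

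**What to change.** If outcome data have not been seen: in SAP 4.1 and Protocol 5.4.1.1, define the primary ANCOVA as adjusted for baseline amblyopic-eye VA and prior amblyopia treatment (yes/no). Use the same covariates in the 8-week model (SAP 4.2.1), and list the acuity-only model as a sensitivity analysis.

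If outcome data have been seen in a cohort, which the revision history makes likely: leave that cohort's primary model as it is. Add the model adjusted for prior treatment next to sensitivity item 4 in SAP 4.1, labelled as supportive and dated.

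Age need not be added. The cost is one sentence and one degree of freedom, with no new data. In the supportive form it also means one more line in the results.
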